noninferiority study that enrolled patients scheduled for elective major open abdominal or orthopedic surgery assessed the proportion of patients who responded “good” or “excellent” at the 48-hour timepoint on the Patient Global Assessment (PGA48) of method of pain control. The results showed that 78.5% vs. 65.6% of patients achieved PGA48 “success” for SSTS vs. IV PCA morphine, respectively, demonstrating non-inferiority as well as statistical superiority for treatment effect. Patients using SSTS reported more rapid onset of analgesia and patient and nurse ease of care and satisfaction scores were higher than IV PCA morphine. Adverse events were similar between the 2 groups, and SSTS had fewer patients experiencing oxygen desaturations below 95% compared to IV PCA morphine. Future studies are needed to determine patient populations that benefit most from the SSTS, assess the added values versus intravenous patient-controlled analgesia, and determine the pharmacoeconomics of the system³.

More recently, a study by Cassavaugh K et al.⁵ analyzed data from a hospital comparing 140 DSUVIA-treated patients with 157 matched historical controls. DSUVIA was dosed either 30 minutes before the end of surgery for longer surgeries or just prior to induction for shorter surgeries. Patients were a combination of inpatient and outpatients (same-day surgery). The data shows an overall 56% decrease in PACU IV morphine milligram equivalents (mean MME \pm SE) opioid requirements compared to control group receiving typical IV opioids (8.1 ± 0.5 to 3.6 ± 0.4 ; $p < 0.001$). The PACU Phase 1 discharge time also was significantly decreased compared to the control group (80 ± 2 min vs 66 ± 2 min; $p < 0.001$). From a safety perspective, 3 patients out of 157 required naloxone in the PACU to reverse respiratory depression in the control group and no naloxone was required in the DSUVIA group. PACU time is estimated to cost between \$6-\$8 per minute, therefore the time saved more than pays for the drug and can increase efficiency and possibly caseload. The investigator’s conclusion is that DSUVIA is a high therapeutic index opioid that has an extended duration of action into the PACU period thereby either

avoiding opioids completely in the PACU in many patients (48.5% of patients in the DSUVIA group vs 16.6% of patients in the control group), or significantly decreasing the amount of IV opioids required in the PACU and therefore decreasing PACU discharge time.

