2. The perioperative use of Dsuvia (sufentanil SL) will be associated with lower overall opioid consumption, lower frequency of rescue opioids, lower PACU and hospital length of stay, and fewer side effects of opioid use (i.e., nausea, vomiting, constipation, respiratory complications) than observed in two historical control groups of patients receiving remifentanil or sufentanil infusions without perioperative Dsuvia.

Methods:

The study design is an Observational Longitudinal (OL) study with historical controls. There will be 1 prospectively recruited study arm (patients receiving the study drug Dsuvia) and 2 historical control arms (one that received an intraoperative remifentanil infusion and the other that received an intraoperative sufentanil infusion, both without Dsuvia).

Inclusion criteria:

[figure not shown]
Patients undergoing spine surgery (1-3 levels) who are opioid-naïve (no opioid use 30 days prior to surgery), 18-75 years old, ASA physical status 1-3.

Exclusion criteria:

Microdiscectomy, chronic opioid users, significant respiratory depression, acute or severe bronchial asthma, chronic lung disease, known or suspected gastrointestinal obstruction including paralytic ileus, liver disease (defined as alkaline phosphatase (ALP) > 56, aspartate aminotransferase (AST) > 100), known allergy or hypersensitivity to sufentanil or its components, baseline dementia, serotonin syndrome, adrenal insufficiency, severe hypotension, increased intracranial pressure, brain tumors, head injury, impaired consciousness, malignant hyperthermia, ASA physical status > 3, age > 75, pregnant patients.

IV. STUDY SCHEMA:

Patients undergoing spine surgery (1 or more levels)

Dsuvia 30mcg SL

Intraoperative Phase

General endotracheal anesthesia (TIVA with propofol/sufentanil)

Standardized anesthetic technique (see protocol below)

Dsuvia x1 prior to emergence from anesthesia

Postoperative Phase

Pain scores (NRS) q15 min up to 2 hrs

Concomitant Medication use/opioid consumption

Dsuvia prn q1hr as 1st line (NRS >3); Fentanyl prn as 2nd line, or 1st

line if repeat Dsuvia cannot yet be given and NRS is >3 (see PACU schema below)

Up to 3 doses of Dsuvia may be administered in the PACU (each at least 1 hr apart)

Hospitalization Phase

Follow up during inpatient hospital stay

Concomitant Medication use/pain scores

Both arms: standard of care analgesia (PO and IV prn)

Quality of Recovery (QoR); patient satisfaction (study arm only)

Post-discharge Phase

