Follow up following discharge

Prescription opioid use

Outcomes:

Primary:

Mean postoperative pain scores (PACU)

Secondary:

Mean postoperative pain scores (inpatient)

opioid consumption (MMEs, PACU and inpatient)

Frequency of opioid rescue medications given

PACU LOS (min)

hospital LOS (days)

nausea, vomiting, constipation, respiratory events

sedation level (PACU)

quality of recovery (QoR 15)

utilization of prescription opioids following discharge

As shown above, the following secondary outcomes will also be collected in the Study cohort to obtain estimates that can be used to power future randomized controlled trials: sedation level, quality of recovery (QoR-15)⁸, patient satisfaction score (satisfaction with the level of pain control, 6-point scale⁴), and utilization of prescription opioids following discharge.

Safety assessments will include adverse events (AEs) and use of concomitant medications, periodic monitoring of vital signs (blood pressure, heart rate, and respiratory rate), and continuous monitoring of oxygen saturation in the PACU.

Detailed Clinical Protocol

Preoperative:

The surgeon will approach the patient and introduce the study and one of the investigators will explain the study to the patient. The surgeon will assess subject at their visit. At this visit, the surgeons will identify any patients that may benefit from Dsuvia. The information will be provided to one of the investigators. The investigator will subsequently review their eligibility and inclusion criteria. If the subject continues to meet all the criteria, the investigator will explain the study with the patient. Thereafter the patients will be provided the consent forms for their review and a 24/7 contact number for any questions regarding this study. All patient questions will be answered and informed consent will be obtained by one of the investigators who is a licensed physician listed on the protocol. The patient will be provided contact information. A co-investigator will be available to answer

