questions on a 24 hour basis. It will be explained to the patient that they will be permitted to withdraw from the study at any time for any reason until their day of surgery. On arrival at the preoperative area, the patient will be assigned a code by one of the investigators. Prior to premedication, all patients will be made familiar with the use of numeric rating scale (NRS): 0-10 (no pain to the worst pain imaginable). The baseline NRS score will be recorded. All routine standard practices for surgery, anesthesia, and perioperative care will be followed with the exception of the study intervention. All patients will be premedicated with midazolam (0.025-0.05 mg/kg)

Intraoperative Management:

The Study arm will receive general endotracheal anesthesia (GETA). Anesthesia induction will be achieved with propofol (1.5-2.5mg/kg), succinylcholine (1mg/kg), and Fentanyl (50-100 mcg) bolus. Anesthesia maintenance will consist of TIVA (total intravenous anesthesia) with continued infusions of propofol (80-200 mcg/kg/min) and sufentanil (0.2-0.3mcg/kg/hr). The study group will receive Dsuvia 30 mcg at surgery end, administered by the anesthesiologist, timed to occur prior to emergence from anesthesia, and after the patient is turned supine. Antiemetic prophylaxis will be administered (ondansetron) per standard practice. The patient will then be transferred to the PACU.

Postoperative Management:

Note that Dsuvia will be ordered as q1hr prn, meaning that repeat doses must be administered at least 1 hr apart (up to 3 doses can be administered in the PACU).

Postoperative pain scores will be recorded by the PACU nurse and the research assistant. This will be obtained by using NRS scale every 15 mins up to 2 hours.

In the PACU, patients will be ordered to receive Dsuvia 30 mcg q1 hr prn for breakthrough pain (for NRS > 3) as the 1st line analgesic, with fentanyl as the rescue analgesic if the patient is still experiencing pain (NRS >3). The following opioid administration schema will be used for pain management in the PACU:

- 1st line: Dsuvia SL 30mcg (NRS >3). 2nd line: Fentanyl 25-50mcg (NRS >3)
- If upon arrival to the PACU the patient is still experiencing pain with NRS >3 but cannot yet receive a repeat dose of Dsuvia (because of having received 1st dose in the OR less than 1 hour ago), then the patient can receive fentanyl 25-50mcg prn until eligible to receive Dsuvia.

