- If at any time the patient's NRS >3 after 20 min following an administration of either Dsuvia or fentanyl, the patient can receive a repeat dose of fentanyl until again eligible to receive Dsuvia.

Once the patient is transferred to the floor, both groups will receive the standard of care postoperative pain management orders (ie PO and IV prn analgesia for NRS > 3).

Patients who require additional doses of Dsuvia will be monitored for respiratory depression for at least one hour after the last administration of the drug dose.

Sample Size/Statistical analysis:

The primary outcome is nurse-collected mean pain scores. Assuming a within-group standard deviation in PACU NRS pain score of 2.5 points⁷, enrollment of 30 patients in the study group and inclusion of at least 80 patients in each retrospective control group will provide at least 80% power at a two sided alpha level of 0.025 (0.05/2 pair-wise comparisons) to detect a minimal clinically important difference of 2 points⁹ between the Study group and each of the retrospective groups using linear regression.

To account for any potential lack of comparability in baseline characteristics between patients in the Study and retrospective groups, all outcomes will be compared between the prospective group and each of the retrospective groups using doubly robust estimation incorporating both multivariable linear regression adjustment and inverse probability of treatment weights based on the propensity score¹⁰. Doubly robust estimation will allow for unbiased treatment effect estimates even if one of the two models (i.e., propensity score model or outcome model) is miss-specified. The multivariable linear regression models for the outcomes will adjust for the following covariates: age, sex, BMI, ASA class, surgical invasiveness tier, reoperation, history of anxiety, anxiolytic use, history of depression, and antidepressant use. Analytic weights will be based on the inverse of the propensity score, calculated via logistic regression as the probability of being in the Dsuvia group conditional upon the aforementioned covariates included in the multivariable outcome model.

Investigator Name/Institution:

[name], MS
Associate Professor of Anaesthesia
Director, Neuroanesthesia

Brigham and Women's Hospital
Harvard Medical School
Department of Anesthesiology, Perioperative and Pain Medicine
[name]
[name]
[contact]
Email: [contact]

Senior Project Manager:
[name]
Email: [contact]

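### Respiratory events are to be compared with historical controls without a shared definition, data source or time window, and the planned covariate adjustment cannot correct unequal ascertainment

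*Combined protocol and SAP*

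**What the plan says.** The design (Methods) is one prospectively recruited Dsuvia arm and two historical control arms, one given a remifentanil infusion and the other a sufentanil infusion.

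- **The claim.** Hypothesis 2 expects "fewer side effects of opioid use (i.e., nausea, vomiting, constipation, respiratory complications) than observed in two historical control groups".
- **The outcome.** The secondary list under Outcomes has the line "nausea, vomiting, constipation, respiratory events" and nothing more. The Purpose section speaks of respiratory effects, the Hypotheses of respiratory complications, and Outcomes of respiratory events. None of the three terms has a threshold, data source or time window.
- **Follow-up of the Dsuvia arm.** Under Outcomes, "Safety assessments will include adverse events (AEs) and use of concomitant medications", together with periodic vital signs and continuous PACU oximetry. Postoperative Management adds: "Patients who require additional doses of Dsuvia will be monitored for respiratory depression for at least one hour after the last administration".
- **The analysis.** Sample Size/Statistical analysis applies doubly robust estimation to every outcome, against each retrospective group, to deal with baseline differences. It uses ten covariates: age, sex, body mass index, ASA class, invasiveness tier, reoperation, and history of and drug treatment for anxiety and depression.

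Outcomes also names four measures collected in the study cohort to help power future trials: sedation, QoR-15, satisfaction and opioid use after discharge. Respiratory events are not among them, so they remain a between-group comparison.

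**The concern.** A comparison of event rates between a cohort followed under a protocol and cohorts reconstructed from charts is only as good as the equality of ascertainment. Here the plan would allow an event noticed by study staff, or during the observation hour after a repeat tablet, to be counted against control events that reached the record through ordinary care.

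The window is a second difficulty. If events are counted over the PACU stay, observation time depends on an outcome that Hypothesis 2 expects Dsuvia to shorten. That could push the comparison the opposite way.

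With criterion, source and window all open, they could also be settled after the control charts have been seen. A difference in either direction, or no difference, would then be hard to interpret. For an opioid that matters, even for a secondary outcome.

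**Working it through.** **1. The plan's own figure.** The only power statement concerns the PACU pain score: 30 against 80 patients, SD 2.5, difference 2, two-sided alpha 0.025.

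- Standard error = 2.5 × √(1/30 + 1/80) = 0.535
- 2 / 0.535 = 3.74; critical value 2.24
- Power = Φ(3.74 − 2.24) ≈ 0.93 (0.927 with the t distribution)

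This agrees with the stated minimum of 80%. It says nothing about respiratory events, for which the plan gives no rate or power.

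**2. The groups side by side.**

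| | Dsuvia arm | Control groups |
|---|---|---|
| Data collection | prospective | retrospective |
| Study adverse-event assessment | yes | not available in retrospect |
| Observation hour after a repeat tablet | yes, if re-dosed | rule cannot apply |
| PACU oximetry and vital signs | yes | not stated; may have been routine |
| Criterion, source, window for the outcome | not stated | not stated |

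The Background reports two different respiratory measures from cited studies. One is naloxone use ("3 patients out of 157 required naloxone in the PACU to reverse respiratory depression in the control group"); the other is oxygen saturation below 95%. The plan adopts neither.

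**3. Why the adjustment does not help.** Let r be the true risk and s the proportion of true events that are recorded, ignoring false positives. For Dsuvia (1) and control (0):

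recorded risk ratio = (r1 / r0) × (s1 / s0)

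Balancing baseline covariates acts on confounding of r1 / r0. The factor s1 / s0 belongs to the group, through the way events are sought and recorded, and no covariate measures that. Having one of the two models correctly specified does not remove it, because both models are fitted to the recorded outcome.

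**4. Illustration.** The documents give no detection rates, so those below are assumptions. True risk is equal in both groups.

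| Detection, Dsuvia | Detection, control | Recorded risk ratio |
|---|---|---|
| 90% | 90% | 1.00 |
| 90% | 70% | 1.29 |
| 90% | 50% | 1.80 |
| 90% | 30% | 3.00 |
| 70% | 90% | 0.78 |
| 50% | 90% | 0.56 |

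A true halving (5% against 10%) with detection of 90% against 50% would be recorded as 0.05 × 0.90 = 4.5% against 0.10 × 0.50 = 5.0%, a ratio of 0.90. Most of a real benefit would be hidden.

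**5. How a PACU-stay window could act.** In one cited study, "The PACU Phase 1 discharge time also was significantly decreased compared to the control group", with means of 66 and 80 minutes. If events occurred at the same constant low rate per minute in both groups, counting only during the stay would give a ratio of about 66 / 80 = 0.83 with no true difference. That study covered mixed surgery, so this shows a possible direction, not a size for this trial. For re-dosed patients the observation hour may pull the other way.

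**The case against.** The strongest reply is that unequal detection has not been demonstrated. The Preoperative section states: "All routine standard practices for surgery, anesthesia, and perioperative care will be followed with the exception of the study intervention". PACU oximetry and respiratory-rate checks may therefore have been the same for everyone. The adverse-event sentence describes no active questioning, so any extra yield over ordinary charting is inferred. The observation rule is a minimum, covers only re-dosed patients, and is sound safety practice. All of this stands, and it limits the point to what cannot be excluded. It does not supply a definition, source or window, and it does not keep study-only detections out of the comparison.

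A second reply is that nausea, vomiting and constipation are equally undefined and sit on the same line. That is fair. The respiratory item is singled out because it alone has a Dsuvia-specific monitoring rule.

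Three stronger readings are tempting but unsupported:

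- **Dsuvia patients are watched longer than controls.** A reader might set the hour after a repeat tablet against the cited control mean of 80 minutes. That compares a minimum for an unknown share of one arm with a mean from a different surgical population. The plan does not say how long spine controls stayed or that the hour must be spent in the PACU.
- **The comparison is biased against Dsuvia.** Closer observation would act that way, but a shorter PACU stay could act in the opposite direction.
- **The comparison is hopeless, or only naloxone will serve.** At the cited 3/157 = 1.9%, 30 patients would yield 30 × 0.0191 = 0.57 naloxone events. That concerns precision rather than ascertainment, comes from another population, and holds only for that measure. The plan sets no significance level for secondary outcomes against which to judge it.

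**Conclusion.** The point holds as a gap in outcome definition and ascertainment for one secondary safety outcome. The plan makes a directional claim about respiratory complications against retrospective controls and sets no common criterion, source or window. It allows study-only detections to enter the comparison, and its adjustment cannot correct the result.

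The size and direction of any bias cannot be computed from the documents. The ratios shown rest on assumed detection rates and indicate only how such a difference would carry through.

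Severity is minor: the primary pain comparison and the sample size are unaffected, and clinical safety monitoring is not in question.

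**What to change.** Before any control chart is read, add one paragraph that does the following:

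1. Defines the between-group respiratory outcome once. Examples are naloxone given for respiratory depression, an airway intervention, or a charted oxygen saturation or respiratory rate below a preset threshold.
2. Takes it from the same routine record fields in all three groups.
3. Counts it over one fixed window from surgery end that is not tied to PACU stay. The length is a clinical choice that the documents do not settle; 24 hours is one option, with the number discharged sooner reported by group.
4. Reports events known only through study adverse-event assessment or the extra Dsuvia observation as Dsuvia-arm safety data, outside the comparison.

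Clinical monitoring and the planned covariate adjustment stay as they are. The same source and window rule could be extended to nausea, vomiting and constipation.

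The cost is a few extraction fields for at least 190 charts (30 + 80 + 80). Some milder events seen only by study staff will leave the comparison, although they are still reported. Charted events will still depend on someone having noticed and recorded them.

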Another recent study, by Tvetenstrand CD et al.⁶ was conducted in a hospital with ambulatory abdominal surgery patients with DSUVIA dosed 30 minutes prior to induction. A total of 47 patients were in the DSUVIA arm and 81 matched historical controls were compared. This study showed a decrease in overall IV opioid requirements and a decreased Phase 1 PACU time. No patients required naloxone for respiratory depression in either group.

Sufentanil is a drug with a rapid onset (15 min) and high potency (30 mg= morphine 5mg) (pka = 8.0 and solubility coefficient greater than 2000). It is highly bioavailable and highly lipophilic with a high therapeutic opioid index (LD50/ED50). It has a much lower Cmax compared with IV sufentanil. It reaches 70 % Cmax in 30 minutes, lasting as long as 3 hours. Based on existing outcomes data, we hypothesize that there will be a clinically significant difference in spine surgery patients as compared to the historical controls.

Purpose:

In this study we plan to examine the perioperative use of Dsuvia (sufentanil SL; FDA approval 2018) in the analgesic regimen for spine surgery, one of the most common surgeries performed in the US. Patients undergoing spinal fusion surgery often experience significant pain during the first three postoperative days⁷. Currently, no data are available for this patient population which routinely experiences moderate to severe acute pain requiring significant opioid use. We will analyze whether Dsuvia (sufentanil SL) is associated with lower pain scores, frequency of rescue

opioids, lower overall opioid consumption, PACU and hospital length of stay, and side effects of opioid use (i.e., nausea, vomiting, constipation, respiratory effects).

Hypotheses:

1. The perioperative use of Dsuvia 30 mcg SL in a prospectively recruited cohort of patients undergoing spine surgery will be associated with lower postoperative numeric rating scale pain scores (NRS; primary outcome) than observed in two historical control groups that did not receive Dsuvia: one group that received intraoperative remifentanil infusion and one that received intraoperative sufentanil infusion.

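### The fixed 0.025 per comparison is valid, but a Holm step-down on the two primary comparisons would be at least as powerful at the same 5% family-wise error

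*Combined protocol and SAP*

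**What the plan says.** Hypothesis 1 (Hypotheses section) predicts lower postoperative pain scores, the primary outcome, "than observed in two historical control groups that did not receive Dsuvia": one given intraoperative remifentanil and one given intraoperative sufentanil.

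The first paragraph of Sample Size/Statistical analysis assumes a "within-group standard deviation in PACU NRS pain score of 2.5 points" and plans "enrollment of 30 patients in the study group and inclusion of at least 80 patients in each retrospective control group". The stated target is that these numbers "will provide at least 80% power" for a true difference of 2 points in each comparison. The significance level behind that figure is a "two sided alpha level of 0.025 (0.05/2 pair-wise comparisons"). The tests themselves are described as "between the Study group and each of the retrospective groups using linear regression".

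The second paragraph of that section describes the analysis: every outcome is compared with each control group by "doubly robust estimation incorporating both multivariable linear regression adjustment and inverse probability of treatment weights based on the propensity score". It states no significance level, testing order or step-down rule. The 0.05/2 in the sample-size sentence is therefore the only multiplicity rule in the document.

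**The concern.** If the planning level is carried into the final tests, each primary comparison must reach p below 0.025 regardless of the other. Suppose one comparison is clearly significant and the other has p between 0.025 and 0.05. Under the fixed split the second is declared negative, although control of the 5% family-wise error does not require it. Once the first null hypothesis has been rejected at 0.025, only one remains, and it can be tested at the full 0.05. Hypothesis 1 names two control groups, so such a result would be reported as half supported when a standard and equally protective procedure would support both parts.

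**Working it through.** **Inputs**, all from Sample Size/Statistical analysis: SD 2.5; 30 Dsuvia patients; 80 in each control group; difference 2 points; two-sided 0.025 per comparison.

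**1. The plan's own figure.**
- SE = 2.5 × √(1/30 + 1/80) = 0.535.
- Expected test statistic at 2 points: 2/0.535 = 3.74.
- Critical value at two-sided 0.025: 2.241. Power = Φ(3.737 − 2.241) = 93.3% (92.7% by the noncentral t with 108 df).

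The claim of at least 80% holds with room to spare.

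**2. Dependence between the tests.** Both comparisons use the same 30 Dsuvia patients. With unweighted means, the correlation of the two test statistics is (1/30)/(1/30 + 1/80) = 0.727.

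**3. The two procedures.**
- Fixed split: reject each null hypothesis if |Z| > 2.241.
- Holm: reject the larger |Z| if it exceeds 2.241; if so, reject the other if it exceeds 1.960 (two-sided 0.05).

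For comparison *i*, Holm adds the probability that 1.960 < |Zᵢ| ≤ 2.241 while the other |Z| exceeds 2.241. It never removes a rejection. With equal effects, the gain in joint power is twice this quantity.

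**4. Results** (bivariate normal, correlation 0.727, unweighted SE):

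| True differences | Both significant: fixed → Holm | At least one (same for both) |
|---|---|---|
| 2.0 and 2.0 | 89.5% → 93.5% | 97.0% |
| 2.0 and 1.5 | 70.4% → 79.1% | 94.1% |
| 1.5 and 1.5 | 61.1% → 70.4% | 81.5% |

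Power per comparison rises from 93.3% to 95.3% at 2 points against both, and from 71.3% to 75.9% at 1.5 against both. The chance of at least one success cannot change, because Holm's first step is the same 0.025 test.

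**5. Error control.** Holm holds family-wise error at or below 5% under any dependence, so the shared arm and the weighting do not threaten it as long as each p-value is itself valid. With one true null and a 2-point effect on the other comparison, the true null is falsely rejected in 2.5% of trials under the fixed split and 4.4% under Holm.

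**6. Sensitivity to weighting.** The power sentence does not allow for the planned inverse probability weights. The document gives no variance inflation, so the factors here are assumptions, and the correlation is held at 0.727. With 2 points against both, joint power from fixed split to Holm is:
- ×1.25: 80.1% → 86.5%
- ×1.5: 70.6% → 78.7%
- ×2: 54.5% → 64.3%

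**The case against.** The strongest reply is that nothing here is wrong. Splitting alpha in two is conventional, gives simple 97.5% confidence intervals, and meets the stated power; even the chance that both comparisons succeed is 89.5%. At the difference the plan calls clinically important, Holm adds 4 points of joint power and 2 per comparison. The larger gains need a true difference below 2 points or an assumed variance inflation. All of this stands, and it limits the point to an improvement.

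It also stands that the document never says a p-value between 0.025 and 0.05 will be called negative. That follows only if the planning level is also the test level. The silence of the analysis paragraph is a further reason to write the rule down.

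Three stronger readings are tempting and should be resisted:
- *The trial is underpowered or alpha is misallocated.* The plan's own inputs show otherwise.
- *The shared Dsuvia arm makes the split wastefully strict, and Holm recovers the slack.* On the unweighted inputs, family-wise error with both nulls true is about 4.2%, but it is the same under Holm, which starts at the same 0.025. Moreover, the correlation under the planned weighted analysis is unknown.
- *Holm costs nothing at all.* It costs no patients and no family-wise error control. However, confidence intervals that match Holm are less simple, and the false rejection rate for a single true null rises as shown in step 5.

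Finally, if Hypothesis 1 is one claim that needs both comparisons, no split is needed: testing each at 0.05 and requiring both gives 93.9% joint power at 2 points, slightly above Holm. The 0.05/2 split suggests two separate claims, but the document does not settle this. Holm serves either reading, since it also allows a valid claim on one comparison alone.

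**Conclusion.** The point holds as an efficiency improvement with a small gain at the design values. The only multiplicity rule in the document is valid but is dominated in power by a step-down procedure with the same 5% family-wise guarantee. At 2 points against both controls the gain is 4.0 percentage points of joint power (93.5 − 89.5) and 2.0 per comparison (95.3 − 93.3), with none for at least one success. It is about 9 points of joint power if both true differences are 1.5.

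These sizes rest on SD 2.5, groups of 30 and 80, a normal approximation and unweighted standard errors. That Holm rejects at least as much and keeps family-wise error within 5% does not depend on those figures. That the fixed 0.025 would govern the final tests is inferred from the sample-size sentence.

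**What to change.** In the analysis paragraph of Sample Size/Statistical analysis, add a sentence, fixed before outcome data are examined: *For the primary outcome, the smaller of the two p-values (Dsuvia against each control group) will be tested at two-sided 0.025 and, if it is significant, the larger will be tested at two-sided 0.05 (Holm).*

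Keep 0.025 in the sample-size sentence as the conservative planning level. The 97.5% intervals can still be reported, with a note that they do not correspond exactly to the Holm decisions. If the sponsor would claim Hypothesis 1 only when both comparisons succeed, the paragraph should say so; testing each at 0.05 and requiring both is then a valid alternative.

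The cost is one sentence: no added patients, no new data, and family-wise error still at or below 5%. The price is the less simple matching intervals and the rise from 2.5% to 4.4% in false rejection of a single true null when the other effect is 2 points.
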